For financial reasons, both for the patient and for society, the government promotes the development of generic drugs at a lower cost and encourages pharmacists to make transition with patients. Many patients using the original Travoprost (Travatan Z) have their treatment modified with generic Travoprost, often without the consent of their treating physician. In Canada, a generic ophthalmic drop with the same active ingredient, at the same concentration as the reference drug, is presumed to be bioequivalent, without the need for a comparative efficacy study. [3]. It is known that Latanoprost, another prostaglandin analogue, may be less stable in generic form than in its original version (Xalatan) under certain conditions. Variations in the concentration of Latanoprost and certain physicochemical properties, such as pH , the material of the container, the size of the drop distributed, are possible which can influence the bioavailability and therefore the effectiveness of the drug [4] [5] [6]. Finally, a variation of the non-medicinal ingredients between the 2 drugs may result in a difference in the type and frequency of the adverse effects, and even affect the efficacy of the product.

In terms of therapeutic efficacy and safety of care, and for reasons of health care costs, it is important to demonstrate whether there is a therapeutic equivalence between generic Travoprost and the brand Travoprost (Travatan Z).

Is this a pilot study? yes no

1a. Review of the literature

Currently, there are many controversies in the literature on the therapeutic equivalence of anti-glaucoma drops and the opinion among experts differ.

Ophthalmic drop may not be as effective as the reference drug, as the efficacy of the generic drug does not need to be proven for market entry in Canada [3].

IOP may be less well controlled with generic Latanoprost, due to variations in the physicochemical properties of the solution, including Latanoprost concentration. These variations are due, among other things, to the properties of the bottle used or the non-medicinal ingredients that differ from the reference medicine [4][5][6][7].

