A 2007 study by Narayanaswamy et al. demonstrated a difference between the generic and original versions of Latanoprost. This pilot study involving 30 patients in a single center in India seemed to demonstrate that generic Latanoprost was less effective than Xalatan in lowering IOP. [8]. However, this is only a small study and some questions about the reliability of the results have surfaced, including concerns regarding the improper storage of the generic Latanoprost used.

On the other hand, several studies have shown an equivalence between the generic drug and the original. A randomized, double-blind study in 2011 by Diguini et al., involving 184 patients, demonstrated the non-inferiority of a generic version of Latanoprost compared to Xalatan.[9]. On the other hand, the generic version used in this study had a composition qualitatively and quantitatively identical to Xalatan, which is often not the case [4][10]. Another randomized multicentre study, by Allaire et al., included 266 patients with diagnosis of primary open angle glaucoma and ocular hypertension. Each patient was assigned to the generic Latanoprost group or the Xalatan group in a ratio of 1: 1. This study demonstrated therapeutic equivalence as well as the same safety profile [11]. Finally, a randomized crossover study by Golan et al. in 2015, compared Glautan, a generic version of Latanoprost, to Xalatan in 19 patients. The hypotensive effect and ocular side effect profile was comparable [12].

2. Objectives

The primary goal was to determine if generic Sandoz-Travoprost is as effective as brand Travatan Z in lowering intraocular pressure, as measured using Goldmann applanation tonometry.

The secondary goal was to determine if patients tolerate generic Sandoz-Travoprost as well as brand Travatan Z, using a questionnaire.

3. Methodology

a. Study Design

Randomized controlled clinical trial, unblinded, crossover trial.

The crossover design was chosen to achieve the power required all the while limiting the number of patients required.

This study was not blinded to reproduce as much as possible the real situation experienced in clinic by the patients and the doctors. The use of masked bottles by the pharmacy was considered. However, some studies have suggested that the different characteristics of drop bottles may have an impact on the size of the drop or the concentration of the drug after 30 days[14]. So it was decided to use the original bottles.

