- Use of other hypotensive ophthalmic drops (except for Travatan Z or generic Travoprost)
- Use of corticosteroid
- To be pregnant
- Breast-feed
- Being monocular
- Have had glaucoma surgery such as trabeculectomy and Tube implants (eg Baerveldt, Ahmed). Patients who have had selective laser trabeculoplasty will also be excluded.
- Active intraocular inflammation
- Ocular surface disease that may interfere with an accurate measurement of IOP
- Any clinically significant eye disease that may interfere with the study

6. Recruitment

The subjects will be adult patients seen in the outpatient ophthalmology clinic of the Hotel-Dieu de Sherbrooke, who require or already use a pharmacological treatment of Travoprost original (Travatan Z) or generic Travoprost and meeting the eligibility criteria.

The subjects will be recruited at the outpatient ophthalmology clinic of the Hôtel-Dieu de Sherbrooke after a new consultation or a follow-up appointment. The physician resident will present the study to the patient, complete the consent form and obtain their signature.

The randomization will be done beforehand.

The only inconveniences for patients, no matter what group they are in, are the 2 follow-up visits, one to 3 weeks and one to 6 weeks.

7. Variables and data collection

Variable	Type	Method of measurement
age	continuous	From the chart
sex	dichotomous	From the chart

ethnic group	categorical	From the chart
diagnostic	categorical	From the chart
IOP	continuous	Goldmann applanation tonometry
initial treatment	dichotomous	From the chart
MD (visual fields)	continuous	Visual field; at the initial appointment
side effects	dichotomous	questionnaire; at the 3 week and 6 week appointments
treatment adherence (number of days missed)	continuous	questionnaire; at the 3 week and 6 week appointments

The data will be collected by the resident in charge of the project, who will be responsible for their management. Registration will be in accordance with the accepted standards of confidentiality as described in the Act respecting health services and social services.

We will use the Goldmann tonometer, a device on the slit lamp, to measure intraocular pressure. Currently, she is the gold standard for measuring intraocular pressure[13].

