The questionnaire given to patients will be a home-based questionnaire designed to check whether patients have had difficulty putting the drops, if they forget to put them on and if they have had adverse effects. The questionnaire will contain a list of side effects that patients can easily identify. The questionnaire will be filled verbally with the patient, and not just read and checked.

The mean deflection index (MD), a parameter given by the automated visual field, is an accepted measure in the literature for stratifying the glaucoma stage, either mild, moderate, or advanced [13].

8. Study Protocol

a. For patients who are new consultations:

At the first visit, the patient's sociodemographic data will be collected and a complete ophthalmic examination will be performed. This examination will include visual acuity, external examination, evaluation of the cornea, anterior chamber, iris, lens, vitreous, retina and optic nerve (with pharmacological dilatation). Intraocular pressure, gonioscopy, pachymetry and visual field Humphrey SITA fast 24-2. If the patient qualifies for the study, resident [name] will present the study. If the patient agrees, resident [name] will complete the consent form with the patient and get his signature. The patient will receive a bottle of original Travoprost (Travatan Z) or generic Travoprost according to the prior randomization. The patient will receive explanations on how to apply the drops.

During the second visit, at 3 weeks +/- 3 days, the IOP will be taken by resident [name] at 9:00 +/- 1h. A bottle of the other medicine will be given to him.

At the third visit at 6 weeks +/- 3 days, the IOP will be taken by resident [name] at 9:00 +/- 1h. The patient will have completed the study and a prescription from Travoprost will be given.

A questionnaire on tolerance and comfort of drops will be completed with the patient at the second and third visit.

b. For patients who were already followed and treated with brand Travoprost (Travatan Z) or generic Travoprost:

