Group 1 (new randomized consultation to receive Travatan Z first)	
 • Presentation of the study to the patient • Obtaining consent • Taking of IOP • A bottle of Travoprost original (Travatan Z) given with instructions to instill a drop at bedtime in the eye reaches 	
 • IOP taken by the resident • Complete the questionnaire on the comfort of the treatment • A bottle of generic Travoprost given with instruction to instill a drop at bedtime in the eye reaches 	
 • IOP taken by the resident • Complete the questionnaire on the comfort of the treatment • End of the study
Group 2 (New Randomized Consultation to Receive Generic Travoprost First)	
 • Presentation of the study to the patient • Obtaining consent • A bottle of generic Travoprost given with instruction to instill a drop at bedtime in the eye reaches 	
 • IOP taken by the resident • Complete the questionnaire on the comfort of the treatment • A bottle of Travoprost original (Travatan Z) given with instructions to instill a drop at bedtime in the eye reaches 	
 • IOP taken by the resident • Complete the questionnaire on the comfort of the treatment • End of the study

Group 3 (Patient already randomized to receive Travatan Z first)
	
 • Presentation of the study to the patient • Obtaining consent • A bottle of Travoprost original (Travatan Z) given with instructions to instill a drop at bedtime in the eye reaches 	
 • IOP taken by the resident • Complete the questionnaire on the comfort of the treatment • A bottle of generic Travoprost given with instruction to instill a drop at bedtime in the eye reaches 	
 • IOP taken by the resident • Complete the questionnaire on the comfort of the treatment • End of the study

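### The side-effect comparison pools new patients with patients already on brand or generic and ignores starting product, so it can shift with the mix of established users enrolled

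*Combined protocol and SAP*

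**What the plan says.** Section 2 sets the secondary objective: to "determine if patients tolerate generic Sandoz-Travoprost as well as brand Travatan Z, using a questionnaire". Section 6 (Recruitment) takes patients "who require or already use a pharmacological treatment of Travoprost original (Travatan Z) or generic Travoprost and meeting the eligibility criteria". That gives three starting states: no travoprost, brand, and generic.

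The variable table in section 7 carries the entry "initial treatment dichotomous From the chart" and does not say what the two levels are. Side effects are collected by questionnaire at weeks 3 and 6 only.

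Section 8b covers brand and generic users under one heading: "For patients who were already followed and treated with brand Travoprost (Travatan Z) or generic Travoprost". The visit table in section 8 has four groups. Groups 1 and 2 are new consultations and groups 3 and 4 are established patients, each split by randomised order. Established patients are not split by the product they were using.

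Section 9a compares the composition of the groups. Sections 9b to 9e then give a paired test, an ANOVA over time, a McNemar test for each side effect and a paired test of compliance. None uses starting product. Section 10 (Limitations) does not mention selection among existing users.

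**The concern.** Someone still taking a product at a follow-up visit may be there partly because it suits them, since those whom it troubled may have stopped or changed. Known allergy is excluded, but the section 5b criteria do not exclude a patient who earlier left the other product because of discomfort. The plan's own background holds that different non-medicinal ingredients could produce different adverse effects, so product-specific intolerance is plausible on its own terms.

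This selection is attached to the product and not to the period. Randomising the order balances period effects but does not change who was enrolled, and pairing within patient does not help either. If most established users are on brand, two equal products can appear to differ against the generic. If most are on generic, the reverse can happen, and a real difference could be masked. Sections 12 and 13 plan to tell patients and pharmacists how the generic compares, so readers should be able to see whether the pooled answer reflects the products or the clinic's prescribing mix.

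**Working it through.** The plan gives no expected side-effect rate for this comparison and no power calculation for it. The 69 evaluable patients in section 5 are sized on intraocular pressure (IOP) and serve here only as the number of pairs.

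**Inputs**
- n, b, g: shares of new patients, brand users and generic users. Not in the documents; assumed.
- p: side-effect rate on either product without selection. Set to 0.30, the lower end of the 30–50% given for ocular hyperaemia in section 3b(iv).
- r: proportional reduction in that rate on the product already in use. Not in the documents; assumed 0.50.
- The two products are truly equal, and tolerance of one is independent of tolerance of the other.

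**Formulas**
- Observed brand rate = p × [n + g + b(1 − r)]
- Observed generic rate = p × [n + b + g(1 − r)]
- False difference, generic minus brand = p × r × (b − g)

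**Worked cases**
- 20% new, 60% brand, 20% generic: brand 0.30 × (0.20 + 0.20 + 0.30) = 21%; generic 0.30 × (0.20 + 0.60 + 0.10) = 27%; difference 0.30 × 0.50 × 0.40 = +6 points, or 69 × 0.06 = 4.1 patients.
- 20% new, 80% brand: brand 0.30 × (0.20 + 0.40) = 18%; generic 0.30 × 1.00 = 30%; difference 0.30 × 0.50 × 0.80 = +12 points, or 69 × 0.12 = 8.3 patients.

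The last column is the share of simulated trials (20,000 per row) in which an exact McNemar test on 69 pairs gave p < 0.05.

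| New / brand / generic | Brand | Generic | Difference | p < 0.05 |
|---|---|---|---|---|
| 100 / 0 / 0 | 30% | 30% | 0 | 3% |
| 50 / 25 / 25 | 26% | 26% | 0 | 3% |
| 50 / 50 / 0 | 22.5% | 30% | +7.5 | 12% |
| 20 / 60 / 20 | 21% | 27% | +6 | 9% |
| 20 / 80 / 0 | 18% | 30% | +12 | 29% |
| 20 / 20 / 60 | 27% | 21% | −6 | 9% |

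**Sensitivity**
- Range of p and r: with p from 0.10 to 0.50 and r from 0.25 to 0.75, the 20/60/20 mix gives 0.10 × 0.25 × 0.40 = 1 point up to 0.50 × 0.75 × 0.40 = 15 points (p < 0.05 in 3% to 36% of trials).
- Shared tolerance: if a fraction f of the selection carries over to the other product, the difference is multiplied by (1 − f). For 20/80/0, f = 0.5 gives +6 points (9% of trials) and f = 1 gives 0 (3%).
- Unequal histories: equal shares cancel only if the histories match. Suppose, at 50/25/25, that the generic users had all tolerated brand before being substituted, so both their rates are reduced alike. Their contribution is then zero, and the brand users alone leave 0.30 × 0.50 × 0.25 = +3.75 points.

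**The case against.** Four points on the other side carry weight.

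First, a reader might infer that a two-level variable cannot hold three starting states. The documents do not support that. Group number already separates new consultations from established patients. If the variable means brand or generic among the established, three states could be rebuilt, provided that a new consultation is always untreated. Section 8b also returns established patients to the medication they started on, so the site must know it. The accurate criticism is that the variable is undefined and is not used in 9b to 9e.

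Second, selection is plausible but not documented. No criterion requires tolerance, control or a minimum time on the product. The background says "Many patients using the original Travoprost (Travatan Z) have their treatment modified with generic Travoprost, often without the consent of their treating physician", which is substitution for reasons other than tolerance. Some generic users may therefore never have been selected for tolerating the generic. This weakens any firm statement of direction, although it also makes matching histories in the two established groups less likely.

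Third, the two products share an active ingredient, so tolerance is probably shared in part, which shrinks the shift. The size should not be overstated from a ratio either. With an 8% rate that disappears completely on the product in use, the 20/60/20 mix gives 0.08 × 0.40 = 3.2% on brand and 0.08 × 0.80 = 6.4% on generic. That is a two-fold ratio, but only 69 × 0.032 = 2.2 patients, and an exact McNemar test on 69 pairs is significant in about 5% of trials.

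Fourth, enrolling current users fits the plan's real-clinic aim, and separate procedures, four groups and section 9a show that starting status was not wholly ignored. That stands. Comparing group composition still does not give a product comparison by starting state.

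**Conclusion.** The concern holds for tolerability, the secondary objective. Three starting states are enrolled, starting treatment is an undefined two-level variable, and the side-effect comparison is pooled without it. If established users are selected for tolerating their own product, that comparison can shift in either direction with the mix enrolled.

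Under the stated assumptions the false difference is +6 points at 20/60/20 and +12 points at 20/80/0. It is zero when mix and histories are balanced, or when tolerance is fully shared. The documents give neither the mix nor the strength of selection, so these are scenarios and not estimates of bias in this trial.

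A reader might extend the argument to efficacy and infer that the generic would look less effective. The documents do not support that step: they say nothing about how well established users were controlled on entry, and the arithmetic here concerns side effects only. The sample size is also unaffected.

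**What to change.** - In section 7, define initial treatment in three levels: none, brand, generic.
- Add one chart item: whether the other product was earlier stopped, and why.
- In 9d, report the generic-versus-brand side-effect comparison by starting state alongside the pooled result, with new patients as the comparison free of prior-user selection. In 9b, give the same breakdown descriptively.
- If the strata point in different directions, limit the tolerability conclusion to the mix of patients enrolled. Agreement across strata should not be a condition for a conclusion, because 69 patients in three strata cannot settle it.

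The cost is one recoded variable, one chart item and a few tables, with no extra patients. The drawback is that estimates within each stratum will be imprecise and must be labelled descriptive.

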At the follow-up visit, if the patient qualifies for the study, resident [name] will present the study. If the patient agrees, resident [name] will complete the consent form with the patient and get his signature. The sociodemographic data of the patient will be collected and a complete ophthalmological examination will be performed. This examination will include visual acuity, external examination, evaluation of the cornea, anterior chamber, iris, lens, anterior vitreous, retina and optic nerve (with pharmacological dilatation). Intraocular pressure, gonioscopy, pachymetry and visual field Humphrey SITA Standard 24-2. Gonioscopy, pachymetry and the visual field could be delayed if they were done in the previous 4 months. The patient will receive a bottle of original Travoprost (Travatan Z) or generic Travoprost according to the prior randomization. The patient will receive explanations on how to put the drops.

During the second visit, at 3 weeks +/- 3 days, the IOP will be taken by resident [name] at the same time as the first visit +/- 1h. A bottle of the other medicine will be given to him.

At the third visit at 6 weeks +/- 3 days, the IOP will be taken by resident [name] at the same time as the first visit +/- 1h. The patient will have finished the study and a prescription of his starting medication will be given.

A questionnaire on tolerance and comfort of drops will be completed with the patient at the second and third visit.

c. For patients who drop out of the study or who are lost to follow-up:

A loss of follow-up of 10% is anticipated so the sample size has been increased by 10%.

d. Management of adverse effects:

The adverse effects of these drugs are well known and are mostly minor and transient. A questionnaire on tolerance and comfort of drops will be completed with the patient at the second and third visit. If, however, a patient is very concerned about an adverse reaction, they may contact the ophthalmology outpatient clinic or contact the resident on call.

Table: Summary of 3 visits by group

	Recruitment day (day 0)	Second visit (at 3 weeks)	Third visit (at 6 weeks)

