
Group 4 (Patient already randomized to receive generic Travoprost first)
	
 • Presentation of the study to the patient • Obtaining consent • A bottle of generic Travoprost given with instruction to instill a drop at bedtime in the eye reaches 	
 • IOP taken by the resident • Complete the questionnaire on the comfort of the treatment • A bottle of Travoprost original (Travatan Z) given with instructions to instill a drop at bedtime in the eye reaches 	
 • IOP taken by the resident • Complete the questionnaire on the comfort of the treatment • End of the study

9. Data analysis

The database will be created with Microsoft Excel.

Statistical calculations will be done with SPSS v20.

a. Comparison of the composition of the different groups

A t-test will be used for continuous variables (if the data are not normally distributed, a Mann-Whitney test will be used).

A Chi-square test will be used for categorical variables (if the frequency is less than 5 for a variable, an exact Fisher test will be used).

b. Comparison of groups at the end of the study

A paired t test will be used if the data is normally distributed (otherwise, a Wilcoxon test will be used).

c. Analysis of the therapeutic effect of drugs

An ANOVA test will be used to compare the effect of the treatments over time (an appropriate transformation will be applied to the data if it is not normally distributed).

d. Comparison of adverse effects between the two treatments

A McNeman test will be used to see if each side effect is as common with both treatments.

e. Comparison of compliance with each treatment

A paired t test will be used to see if patients have the same compliance for each treatment (Wilcoxon test if non-normal data).

10. Limitations

There is a potential bias of information if a patient believes that the generic is less effective, which could lead to a decrease in compliance or a change in dosage by the patient (eg: he could put it twice a day and not once). To counter this bias, the importance of abiding by the prescribed posology will be explained to patients.

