To avoid a learning bias, patients who start topical treatment for the first time will be told how to instill the drops during the initial outpatient visit. This instruction will be given by the resident to show the correct way to instill eye drops. A practice will then be performed using a new bottle of artificial tears. For those who are already taking Travoprost (Travatan Z) or generic Travoprost, they will be asked, during their first outpatient visit, to demonstrate how they instill their gout using a new bottle of artificial tears. If necessary, they will receive a short lesson given by the resident.

The loss to follow-up, inevitable in a prospective study, would lead to an information bias. The sample size has therefore been increased by 10%.

11. Ethical considerations

Adverse effects related to the use of Travoprost, as well as the patient's required time and movement, are the only real disadvantages. Follow-up will be provided by the treating team.

12. Anticipated benefits

With the information obtained as to the equal or lesser effectiveness of generic Travoprost compared to the original Travoprost (Travatan Z), we will be able to better inform patients asking if the generic version of their ophthalmic drop is equivalent reference drug. If we find equal efficiency, the savings could be remarkable. However, if we find less efficiency, then we

can ensure that the Travoprost served to our patients is the original Travoprost (Travatan Z) and not a generic, ensuring better control of IOP and therefore better control of the disease.

13. Dissemination of results

We hope to publish the results of this study in a specialized journal in ophthalmology and present them at local, national and international conferences. The results could also be communicated to pharmacists, to raise awareness of the effectiveness (or lack of effectiveness) of generic Travoprost.

14. Schedule

2015/08 Submission to the Scientific and Ethics Committees

2016/07 Start of patient recruitment

2017/07 Data analysis

2017/10 Writing and publication of the article

15. Budget

The cost of the study will be solely due to the ophthalmic drops delivered to patients.

Sample size:	69
Loss to follow-up:	10%
Increased sample size to compensate for anticipated loss to follow-up:	76
Cost per bottle of generic Travoprost (5mL):	\$44.99
Cost of generic Travoprost with taxes	\$51.74
Bottles of generic Travoprost per patient	1
Total per patient (including taxes):	\$51.74

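### A patient who leaves because of a reaction has no side-effect record for the product in use and does not enter the tolerability tests in section 9d; a larger sample does not correct this (minor).

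*Combined protocol and SAP*

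**What the plan says.** Section 2 sets one secondary goal: "The secondary goal was to determine if patients tolerate generic Sandoz-Travoprost as well as brand Travatan Z, using a questionnaire". The variable table in section 7 gives the source of the side-effect data as "questionnaire; at the 3 week and 6 week appointments". Section 8 ties the questionnaire to the second and third visits for new and established patients alike. Section 7 adds: "The questionnaire will be filled verbally with the patient, and not just read and checked".

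Section 8c, headed for patients who drop out or are lost, consists of one sentence: "A loss of follow-up of 10% is anticipated so the sample size has been increased by 10" per cent. Section 10 returns to the subject: "The loss to follow-up, inevitable in a prospective study, would lead to an information bias". Its answer is again the 10% increase.

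For reactions between visits, section 8d offers a contact route: "If, however, a patient is very concerned about an adverse reaction, they may contact the ophthalmology outpatient clinic or contact the resident on call". Section 11 says: "Follow-up will be provided by the treating team". Neither section says that such a contact is entered as study data.

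The analysis is in section 9d: "A McNeman test will be used to see if each side effect is as common with both treatments". The plan gives no rule for a missing questionnaire, and no variable records why a patient left.

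**The concern.** Leaving because a drop is not tolerated bears directly on the secondary goal, yet it is the event this plan does not collect. Someone who stops coming does not complete the questionnaire for the product that caused the trouble, and nothing else in the plan supplies the information.

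The remedy in sections 8c and 10 replaces patients; it does not recover what the leavers experienced. If one product drives out more patients than the other, the planned tests are made on those who stayed. The information also cannot be reconstructed reliably after the trial, so the decision belongs in data collection rather than in the analysis.

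The trial intends to tell patients and pharmacists whether the generic matches the brand. As written, it could not say how many patients left each product because of a reaction.

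**Working it through.** **1. Who falls out of 9d.** McNemar's test needs a yes/no answer under both products from the same patient.

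| Patient | First product | Second product | In 9d? |
|---|---|---|---|
| Attends both visits | recorded | recorded | yes |
| Leaves in period 2 | recorded | none | no |
| Leaves in period 1 | none | never given | no |

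The plan does not state the restriction to complete pairs. It follows from the choice of test and the lack of a missing-data rule. Patients who telephone the clinic or skip drops but still attend are not part of the gap, because the side-effect and days-missed items cover them.

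**2. How many.** Section 5 gives 69 evaluable patients and 76 enrolled. The plan's figure reproduces as 69 × 1.10 = 75.9, rounded up to 76. The implied loss is 76 − 69 = 7. Ten per cent of 76 is 7.6, leaving 68.4. So about 7 to 8 patients lack a pair.

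**3. Size of the unreported difference.** Suppose k leavers left because of a reaction, all on one product (an assumption; the documents give no causes). The unreported difference is k/76:

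- k = 0: 0 points
- k = 1: 1.3 points
- k = 3: 3.9 points
- k = 7: 9.2 points
- k = 8: 10.5 points

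If the k patients split equally between products, it is zero.

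**4. Effect on one test, completers balanced.** Assume m discordant pairs in each direction among completers, so the planned test gives p = 1.0. Now add k period-2 leavers who all had the effect on the same product and not on their first. The exact two-sided p is 2 × P(X ≥ m + k), with X binomial (2m + k, 0.5).

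| | m = 0 | m = 5 | m = 10 |
|---|---|---|---|
| k = 3 | 0.25 | 0.58 | 0.68 |
| k = 7 | 0.016 | 0.14 | 0.25 |
| k = 8 | 0.008 | 0.096 | 0.18 |

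The values of m and k are assumptions. Take 0.05 as the threshold (section 5 gives it for the sample size; 9d states none). At least six such leavers are then needed even with no discordant completers: 2 × 0.5⁵ = 0.063, but 2 × 0.5⁶ = 0.031. With k = 7, p is below 0.05 only for m = 0 or 1 (8 vs 1 gives 0.039; 9 vs 2 gives 0.065).

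**5. Direction.** Suppose instead that completers show 8 brand-only and 5 generic-only reports. The planned test then shows a difference of 3/69 = 4.3 points against the brand (p = 0.58). If three period-2 leavers had the effect on the generic only, the full count would be 8 vs 8 (p = 1.0). Here, leaving them out creates an apparent difference rather than hiding one.

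**The case against.** The strongest case against the point concerns its consequence. The documents give no sign that any loss would be reaction-related. Known allergy is excluded, each period lasts three weeks, many patients already use travoprost, and section 8d describes the reactions as usually mild and short-lived. The significant cases in the table are contrived: six or more leavers, all in period 2, all on one product, all with the same effect, and almost no discordant completers. All of this stands, and it is why the point is minor.

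Three defences of the plan are weaker.

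- **A leaver's reaction might reach the chart through 8d or the treating team.** It might, and nothing forbids such a note. But section 7 takes only age, sex, ethnic group, diagnosis and initial treatment from the chart, so the note would not become study data.
- **Section 7 calls the questionnaire home-based, so a leaver might have filled it in.** The same paragraph has it completed orally with the patient, section 8 ties it to the visits, and no return route is given.
- **The goal is tolerability by questionnaire, so discontinuation would be a new endpoint.** That is partly fair. But those who leave lack the questionnaire itself, and section 10 already accepts that losses cause bias.

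A reader might infer three stronger things that the documents do not support. The first is that 9d must lean towards equal tolerability; step 5 shows that this depends on the completers. The second is that 7/76 = 9.2 points is a ceiling; 10% of 76 is 7.6, so eight losses fit the plan's own rate, and actual losses could be higher. The third is that the primary IOP result is at stake; this point gives no ground for that.

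**Conclusion.** The concern holds as a minor point. Following section 8c as written, the trial collects no side-effect data from a patient about the product he or she was using when leaving, and the only planned side-effect comparison omits that patient. Enlarging the sample does not correct the bias that section 10 acknowledges.

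If reaction-related losses differ by product, 9d can misstate the comparison in either direction; with balanced completers it conceals the difference. The size is unknown and may be zero. At the planned loss it concerns 7 to 8 of 76 patients, at 1.3 points for each reaction-related leaver on one product. With balanced completers a test result would change only in extreme configurations. A result already at the threshold could be tipped by one patient (5 vs 0, p = 0.063, becoming 6 vs 0, p = 0.031), but nothing in the documents makes that likely.

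The conclusion rests on two readings: that 9d uses complete pairs, and that data sources not listed in section 7 will not be used.

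**What to change.** **Sections 7 and 8c.** For each patient who withdraws or misses a visit and still agrees to contact, the project resident makes one telephone call. Record the date, the product in use, the reason for leaving (reaction, other, not reached) and the answers to the existing side-effect list for that product. The list is already asked orally, so it transfers to the telephone.

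**Reporting.** Tabulate those who left because of a reaction, by product, among all patients given that product. The denominator is 76 if every loss falls in period 2, and as low as 68 for one product if eight patients leave in period 1 before receiving it. Show patients not reached as a separate category, so that a zero count is not mistaken for evidence that nobody left for that reason. Period-1 leavers can appear only in this table.

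**Section 9d.** Add one sentence saying that the McNemar tests describe patients with both questionnaires.

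A separate log of unscheduled contacts and a repeat McNemar analysis with telephone answers are not needed to close this gap.

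**Cost.** About 7 to 8 calls by existing staff, one short table and possibly an ethics notification. Consent pages are not in the text reviewed, so what patients agreed to about contact after withdrawal could not be checked. Stated reasons in an open-label trial may be coloured by beliefs about the generic, a risk that section 10 already recognises, and telephone answers follow a shortened exposure. With so few events the table is descriptive only.
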